7.2. Reactogenicity Endpoints

Subjects are excluded from the analysis of reactogenicity if they did not receive a particular vaccine dose or if the data are missing on all days of the interval.

Reactogenicity data will be collected through e-Diary, which does not allow subjects to skip individual questions. Therefore, for a specific day, as long as the e-Diary data is transferred for that day, all of the reactogenicity data for the subject on that day is considered complete. The e-Diary completion status will be summarized per [Section 6.3.1](#). The e-diary completion summary will provide the missing data information on reactogenicity data.

Based on data from available studies, missing data on reactogenicity is minimal, which is consistent with Li et al. (2011).² No sensitivity analysis is planned for reactogenicity data.

7.3. CRF Safety Data

Subjects are excluded from the analysis if they do not receive a particular vaccine dose or if safety data are missing.

The sponsor is making every effort to follow up with subjects for safety data (6 months after the last vaccination). Data from previous studies showed a small proportion (5%) of subjects not being contacted via telephone or did not finish the full series of 3 doses of the vaccinations. The missing data rate on the safety data among each analysis interval will be summarized for each group. The numerator will be the # of subjects with missing CRF safety data information. The denominators vary with the analysis interval.

Table 11. Denominators for Safety Data Analysis Intervals

#	Analysis Interval	Denominator
1	Within 30 days of vaccination 1	# of subjects received vax 1
2	Within 30 days of vaccination 2	# of subjects received vax 2
3	Within 30 days of vaccination 3	# of subjects received vax 3
4	Within 30 days of any vaccination	# of subjects received any vax
5	During the vaccination phase	# of subjects received any vax
6	During the follow-up phase	# of subjects received any vax
7	Throughout the study	# of subjects received any vax

8. STATISTICAL METHODOLOGY AND STATISTICAL ANALYSES

8.1. Statistical Methods

Unless otherwise explicitly stated, descriptive statistics for continuous variables are: n, mean, median, standard deviation, minimum and maximum. Descriptive statistics for categorical variables are: n, percentage, and total (N).

8.1.1. Analyses for Continuous Data

For each of the 4 primary strains, hSBA titers will be logarithmically transformed for analysis and Geometric mean titers (GMTs) will be computed with 95% confidence intervals (CI) for each group. The 2-sided, 95% CI for the GMTs will be constructed by back transformation of the confidence intervals for the mean of the logarithmically transformed titers computed using the Student t distribution.

8.1.2. Analyses for Binary Data

8.1.2.1. Immunogenicity Data

All of the binary immunogenicity endpoints will be descriptively summarized along with the exact 2-sided 95% confidence interval (or Clopper-Pearson confidence limit) for the proportion.

The exact confidence interval for proportion will be computed using the F distribution. If r equals the number of responses and n equals the number of subjects, then it follows that $p = r/n$ is the estimate of the proportion of responses. An exact 95% confidence interval can be computed by solving the following 2 equations. For the lower limit p_L , use

$$p_L = \frac{rF_L}{(rF_L + (n - r + 1))} \quad \text{and for the upper limit } p_U, \text{ use} \quad p_U = \frac{(r + 1)F_U}{(n - r) + (r + 1)F_U}$$

where F_L is the quantile from the F distribution for $\alpha=0.025$, with numerator degrees of freedom equal to $2r$ and denominator degrees of freedom equal to $2(n-r+1)$. F_U is the quantile from the F distribution for $\alpha=0.975$, with numerator degrees of freedom equal to $2(r+1)$ and denominator degrees of freedom equal to $2(n-r)$. When r equals 0, F_L should be set equal to 1.0 so p_L equals 0. When r equals n , F_U should be set equal to 1.0 so p_U equals 1. The confidence interval using the F distribution is described in Collett (1991).³

8.1.2.2. Safety Data

The proportion of subjects reporting immediate AEs and reporting reactogenicity events and by severity will be summarized and compared between Group 1 and Group 2. The difference in the percentages (Group 1- Group 2) and 2 sided 95% exact CIs for the difference will be provided with p-values. The exact CIs will be computed using the noninferiority procedure of Chan & Zhang,⁴ using the standardized test statistic and gamma=0.000001.

Fisher's Exact test will be used to compare the endpoints of AE, SAE, medically attended AE and newly diagnosed medical conditions. The difference in the percentages (Group 1- Group 2) and 2 sided 95% CIs for the difference will be provided. The CIs of the

difference will be computed using the Miettinen-Nurminen⁵ method. The confidence intervals and statistical tests presented for the safety data will not be used to test hypotheses but will be used to determine which events may need further clinical investigation. No adjustment for multiplicity is needed.

8.2. Statistical Analyses

8.2.1. Analysis of Primary Endpoints

The primary analysis for the primary objectives will be based on the evaluable immunogenicity population. 95% confidence intervals (CIs) for the percentage of subjects with hSBA titer \geq LLOQ to each of the 4 primary strains at 1 month postdose 3 will be presented, along with the response rate. To address the two primary objectives, these data will be presented in the 2 age strata, \geq 24 months to $<$ 4 years and \geq 4 years to $<$ 10 years.

To support the interpretation of the primary analyses, an identical analysis based on the mITT population will be conducted.

As described in [Section 7.1](#), depending on serology testing strategy, a further supportive analysis of the primary endpoints will be done using the MMRM model, in the evaluable population.

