## **9.2. Immunogenicity Analysis**

This is not a hypothesis-testing study; thus, an estimation approach will be used to assess the primary, secondary, and exploratory objectives.

As assay data are expected to be missing completely at random (MCAR) (Scott & Hsu, 2011), the primary analysis for the primary objectives will be based upon the observed, determinate observations. If all subjects have hSBA tested for all of the 4 primary MnB test strains, descriptive summaries will be provided to describe the hSBA data missing reason and the relationship between the missing data indicator and other design variables or covariates (age, race, gender, center, etc) and the observed hSBA data. Additionally, a sensitivity analysis using mixed effects model with repeated measurement (MMRM) will be applied to the primary endpoints. The MMRM uses the maximum likelihood estimation, and it is under the assumption that the missing is at random (MAR). If 50% of the subjects or less have 2 strains tested and the remaining have the other 2 strains tested, no sensitivity analyses will be planned because the missing assumption is MCAR.

For the calculation of GMTs, hSBA results below LLOQ will be set as  $\frac{1}{2}$  of LLOQ as primary analysis.

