5. ANALYSIS SETS

5.1. Full Analysis Set

The intent-to-treat (ITT) population includes all subjects who are randomized. All randomized subjects who have at least 1 valid and determinate assay result related to a proposed analysis will be included in the modified intent-to-treat (mITT) population. This analysis set is for the immunogenicity analysis. Subjects will be analyzed according to the investigational product to which they were randomized.

5.2. 'Per Protocol' Analysis Set

The evaluable population will be the primary population for the immunogenicity analyses. To be included in the evaluable population for the primary immunogenicity endpoint, subjects will have to meet all the following criteria:

1. Randomized into the study,
2. Were eligible, ie, satisfied all inclusion/exclusion criteria, through 1 month post vaccination 3,
3. Received all the scheduled investigational products at study visits 1, 3 and 5 as randomized,
4. Have baseline blood drawn prior to the first dose of vaccine and have post-vaccination 3 blood draw (Visit 6) within 28-42 days after vaccination 3 (Visit 5). (The interval day will be calculated as blood draw date – vaccination date),
5. Had a valid and determinate assay results for the proposed analysis, and
6. Had no important protocol deviations.

An important protocol deviation is a protocol deviation that, in the opinion of the sponsor's global medical monitor, would materially affect assessment of immunogenicity, eg, subject receipt of a prohibited vaccine or medication that might affect immune response or a medication error with suspected decrease in potency of the vaccine. The sponsor's global medical monitor will identify those subjects with an important protocol deviation before any immunogenicity analysis is carried out.

Subjects will be analyzed according to the investigational product to which they were randomized.

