7. HANDLING OF MISSING VALUES

7.1. Immunogenicity Data

For the hSBA assay results, the following values will be set to missing: QNS (insufficient sera), indeterminate results, and Not Done. Subjects without a blood draw (eg, dropouts) will also have missing immunogenicity data.

The primary immunogenicity analyses will use only valid and determinate assay results with no imputation of missing values, which uses the assumption that data are missing completely at random (MCAR).¹ The approach to missing assay data depends on serology testing strategy, to be determined:

- If volume permits, subjects will have serum tested for all 4 primary strains by hSBA. In this case, descriptive summaries will explore the relationship between the missingness indicator and design variables or covariates (age, race, gender, site etc.). A sensitivity analysis using a mixed effects model with repeated measurement (MMRM) will be applied to the primary immunogenicity endpoints.

- If only 50% of subjects are tested for 2 of the 4 primary strains, and the other 50% of subjects tested for the other 2 primary strains, there will be no sensitivity analysis. Data will be assumed to be MCAR.

For the calculation of GMTs, hSBA values below LLOQ will be assigned a value of half the LLOQ. The LLOQ for CCI (A22) is 1:16, and for the other 3 primary test strains is 1:8.

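### If all four strains are tested, the MMRM meant to check the missing-data assumption for the primary proportions is run in a population that has already removed the dropouts

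*SAP*

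**What the plan says.** Protocol 9.2 and SAP 7.1 base the primary immunogenicity analysis on valid, determinate results without imputation, and state that this assumes MCAR. SAP 7.1 counts subjects without a blood draw, giving dropouts as the example, among those with missing data.

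What follows depends on testing. If only two strains are tested in each half of the subjects, both documents say openly that no sensitivity analysis is planned. If all four strains are tested, Protocol 9.2 says that "a sensitivity analysis using mixed effects model with repeated measurement (MMRM) will be applied to the primary endpoints" and describes it as valid under MAR. SAP 7.1 repeats the commitment: "A sensitivity analysis using a mixed effects model with repeated measurement (MMRM) will be applied to the primary immunogenicity endpoints". SAP 8.2.1 names the population: "depending on serology testing strategy, a further supportive analysis of the primary endpoints will be done using the MMRM model, in the evaluable population".

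The evaluable population is defined in SAP 5.2. Criterion 3 is "Received all the scheduled investigational products at study visits 1, 3 and 5 as randomized". Criterion 4 requires a Visit 6 draw 28 to 42 days after dose 3. Criterion 5 is "Had a valid and determinate assay results for the proposed analysis".

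SAP 8.2.1 also repeats the primary analysis, unchanged in method, in the mITT population. SAP 8.2.4.2 specifies an MMRM of log titers in mITT, for the age strata combined.

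**The concern.** A MAR model improves on an observed-case proportion only if it contains subjects who lack the Visit 6 result but have results at other visits. Their earlier titers are what move the estimate. If such subjects are filtered out first, the two estimates agree because of how the set was built, and that agreement could be reported as evidence that missing data did not matter.

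The plan does not treat departures from MCAR as impossible. Protocol 9.2 calls for summaries of "the relationship between the missing data indicator and other design variables or covariates (age, race, gender, center, etc) and the observed hSBA data". In the current SAP this MMRM is the only model-based check of the primary proportions, and no section writes out a model for that binary endpoint.

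**Working it through.** **The plan's own count.** Four strains in all subjects: 400 × 4 strains × 4 visits = 6,400 results. Half-testing: (200 × 2 + 200 × 2) × 4 visits = 3,200. Both match SAP 2.1.3. The MMRM belongs to the 6,400 case. Group 1 has 400 × 3/4 = 300 subjects, so 150 per age stratum.

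**Who is left for the model to adjust for.**
- Dropout before dose 3: removed by criterion 3.
- No Visit 6 blood after dose 3: removed by criterion 4.
- Visit 6 blood drawn, but no valid result for a strain: depends on criterion 5. Applied per strain, these subjects go too. Applied per subject, they stay, and strain-level serum or assay failures are all that remains to be modelled.

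On neither reading does a subject without Visit 6 blood contribute a row.

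**What the model then returns.** On the per-strain reading Visit 6 is complete. With free visit means and an unstructured covariance, the likelihood factors into f(Visit 6) × f(other visits | Visit 6), and only the first factor carries information on the Visit 6 mean. The maximum likelihood estimate is therefore the observed proportion. With age in the model, the same holds at the mean age. Simulation (n = 140, 8% missing at other visits, 300 runs) gave a maximum difference of 0.0 points. A random-intercept logistic model (150 runs) differed by at most 0.18 points.

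**Bounds that need no missingness mechanism** (150 per stratum; response near 80% assumed). With r responders among n observed, the full-sample proportion lies between r/150 and (r + 150 − n)/150.

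| Missing | Observed | Exact 95% CI | Full-sample range |
|---|---|---|---|
| 8 (5%) | 114/142 = 80.3% | 72.8–86.5% | 114/150 = 76.0% to 122/150 = 81.3% |
| 15 (10%) | 108/135 = 80.0% | 72.3–86.4% | 108/150 = 72.0% to 123/150 = 82.0% |

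The 5% is from SAP 7.3 (not reached by telephone, or series not finished). The 10% is an assumption.

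**Illustrations under assumed mechanisms.**
- Large sample: true rate 80%, Visit 4 to Visit 6 correlation 0.7, loss after Visit 4 likelier at low Visit 4 titer (logit slope −1 per SD). At 5%, 10% and 20% loss the observed rate is 81.03%, 82.15% and 83.95%. Maximum likelihood inside the evaluable set gives 81.11%, 82.20% and 83.91%. Using everyone with Visit 4 data gives 79.97%, 80.06% and 80.02%.
- Milder: n = 150, true rate 80%, dropout before dose 3 with an odds ratio of 3 for Visit 4 non-response, plus age-related assay gaps. The observed rate is too high by 0.37 points at 8% missing and 0.67 at 14%. The evaluable-set model leaves all of that on the per-strain reading, and 0.31 and 0.61 on the per-subject reading. The mITT model leaves −0.01 and −0.03. With an odds ratio of 1 the observed bias is at most 0.12 points.

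**The case against.** The strongest reply is about the estimand. The endpoint is response one month after the third vaccination, and a child who never received dose 3 has no such response. In the milder simulation most of the bias comes from dropout before dose 3: 0.31 of 0.37 points and 0.61 of 0.67. Only 0.06 points in each case come from assay gaps. This stands. A modelled value for those children is hypothetical and must be labelled so. For three-dose recipients what is left is loss between Visits 5 and 6 and assay failure, and the documents give no rate for either.

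A reader might also infer that the check fails for out-of-window draws and for missed-dose subjects who still gave Visit 6 blood. The documents do not support that. Those results exist; the per-protocol rules exclude them, so MCAR is not at issue, and the observed-case mITT repeat in SAP 8.2.1 restores them. Nor should the MMRM be said to test MCAR. It gives a MAR-based estimate to set beside the observed one.

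Nor does the SAP ignore missingness. SAP 8.2.4.1 summarizes a missing-data indicator against covariates and GMTs, and SAP 8.2.4.2 fits a maximum likelihood model of titers in mITT, whichever testing strategy is used. Both are useful. But the first gives no adjusted estimate, and the second concerns GMTs in combined strata, not proportions by stratum.

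**Conclusion.** The point holds for dropouts without Visit 6 blood and, if criterion 5 is applied per strain, for missing Visit 6 assay results. For them the population named in SAP 8.2.1 defeats the purpose stated in Protocol 9.2 and SAP 7.1. This follows from the definitions and needs no assumed rate.

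Its importance is minor. The analysis is supportive and runs only under four-strain testing, which itself implies that serum was mostly sufficient. The trial has no hypotheses or decision rules. At 5% missing, even the extreme bounds stay inside the exact CI; at 10% the lower bound (72.0%) falls just below it (72.3%).

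The documents do not show that the primary estimates are biased. The simulated biases, from hundredths of a point to several points, rest on response rates, correlations and dropout mechanisms that the documents do not give, and the 5% loss figure describes safety follow-up and series completion, not missing immunogenicity data.

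**What to change.** In SAP 8.2.1, with a matching line in SAP 7.1:

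1. Run this MMRM in the mITT population instead of the evaluable population, and spell out that for this analysis it means every randomized subject with a valid, determinate result for that strain at one or more of Visits 1, 4, 6 and 7. The explicit wording matters because SAP 5.1 defines mITT as "All randomized subjects who have at least 1 valid and determinate assay result related to a proposed analysis", a restriction that Protocol 9.3 lacks. If it were taken to mean a Visit 6 result, changing the population's name alone would achieve nothing.
2. State that the dependent variable is the response indicator (hSBA at or above LLOQ) at each visit, modelled by strain and age stratum with visit and age at randomization.
3. Report the modelled Visit 6 proportion and its 95% CI beside the observed proportion.
4. Say that modelled values for subjects without dose 3 are hypothetical, and repeat the analysis in subjects who received all three doses.

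The cost is SAP wording and a few supportive fits: 4 strains × 2 strata = 8, and 8 more for the three-dose repeat. No new data are needed and the primary analysis is unchanged.

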8.2.4.2. Assessing Factors of Age, Race, Center, and Gender on GMT

A mixed-effect model with repeated measurement (MMRM)⁶ will be utilized to assess the effect of age, race, center and gender, in which both baseline and the postvaccination titers (in logarithmic scale) are modeled as dependent variables for each primary strain. This model is using maximum likelihood estimation, therefore, it also serves as a sensitivity analyses on missing data for the GMT. To account for the intrasubject correlation among the repeated measures, an unconstrained covariance matrix will be used. In case the model does not converge, further covariance structures will be explored (eg, autoregressive, compound symmetry).

Log (hSBA) = Group + center + race + gender + age at randomization +visit+ Group* visit.

The intercept will be set as a random effect.

Site may be used as centers. However, several sites maybe pooled to one center depending on geographic location (if size <5 within the site). In the case of non-convergence, country may be used as center.

In addition to Type III analysis output, least squares GMT at each visit for each group will be summarized for each strain.

This analysis will only be applied to subjects in the combined age strata in the mITT population, using $\frac{1}{2}$ LLOQ to impute the hSBA values below LLOQ.

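### The MMRM promised as a sensitivity analysis of the primary proportions has no specified model that returns them, and its stated population leaves almost nothing missing to address

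*SAP*

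**What the plan says.** **Primary endpoints.** SAP 6.1.1 and Protocol 2.2.1 define them as proportions at or above LLOQ for each of 4 strains, 1 month after dose 3, separately for children aged 24 months to under 4 years and 4 to under 10 years. SAP 8.1.2.1 fixes the method: "All of the binary immunogenicity endpoints will be descriptively summarized along with the exact 2-sided 95% confidence interval". SAP 8.2.1 fixes the level: "To address the two primary objectives, these data will be presented in the 2 age strata".

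**The promise.** When all 4 strains are tested, Protocol 9.2 says "a sensitivity analysis using mixed effects model with repeated measurement (MMRM) will be applied to the primary endpoints", and explains that the model rests on MAR rather than MCAR. SAP 7.1 repeats it: "A sensitivity analysis using a mixed effects model with repeated measurement (MMRM) will be applied to the primary immunogenicity endpoints". SAP 8.2.1 adds the population: "a further supportive analysis of the primary endpoints will be done using the MMRM model, in the evaluable population". If each half of the children is tested on only two strains, both documents plan no sensitivity analysis.

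**The only MMRM written out.** SAP 8.2.4.2 gives "Log (hSBA) = Group + center + race + gender + age at randomization +visit+ Group* visit", fitted per strain to baseline and postvaccination log titers. It limits the scope: "This analysis will only be applied to subjects in the combined age strata in the mITT population". Its outputs are Type III tests and least squares GMTs by visit and group. The section describes its own missing-data role as one for the GMT.

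**The concern.** A sensitivity analysis has to target the same quantity as the analysis it supports. Here the endpoint is a proportion within an age stratum, and the one specified model estimates a mean log titer over both strata. Neither the protocol nor the SAP says how to get from one to the other: no link function, no stratum handling, no rule for turning a fitted titer distribution into a share at or above LLOQ.

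The primary analysis uses observed, determinate results and assumes MCAR. The MMRM is the only planned step that would relax this for the primary endpoints. A programmer following the SAP would produce either a GMT table that does not bear on the primary proportions, or a model invented at the analysis stage.

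**Working it through.** **1. The plan's own figures.** SAP 2.1.3 gives about 3,200 hSBA results under split testing and about 6,400 if all strains are tested in everyone. 400 × 2 strains × 4 visits = 3,200; 400 × 4 × 4 = 6,400. Both reproduce. The second case triggers the MMRM. Group 1 then has 400 × 3/4 × 1/2 = 150 children per stratum for every strain before exclusions (75 under split testing). No figure is attached to the MMRM itself.

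**2. Endpoint and model side by side.**

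| | Primary endpoint | MMRM promised for it (SAP 8.2.1) | MMRM specified (SAP 8.2.4.2) |
|---|---|---|---|
| Outcome | titer ≥ LLOQ, yes/no | not stated | log titer |
| Age level | each stratum | not stated | combined only |
| Population | evaluable | evaluable | mITT |
| Output | proportion, exact CI | not stated | least squares GMT |

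**3. Does a GMT determine the proportion?** Constructed titers (assumed, for illustration): LLOQ 1:8, values below it set to 4, n = 150.

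- Set A, 30 at 4 and 120 at 128: mean log2 titer = (30×2 + 120×7)/150 = 6, GMT = 2^6 = 64; 120/150 = 80% (exact 72.7 to 86.1%).
- Set B, all at 64: GMT 64; 150/150 = 100% (97.6 to 100%).
- Set C, 60 at 4, 30 at 256, 60 at 512: (60×2 + 30×8 + 60×9)/150 = 6, GMT 64; 90/150 = 60% (51.7 to 67.9%).

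The GMT is the same and the proportions span 40 points. Reading a proportion off a fitted normal does not rescue this. With P = Φ((mean − 3)/SD) on the log2 scale, Set A (SD 2.007) implies 93.3% against an actual 80%, and Set C (SD 3.297) implies 81.9% against 60%.

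**4. Does a pooled result determine the strata?** With 150 per stratum, true pairs of 80/80, 70/90 and 60/100% all pool to 240/300 = 80% (exact 75.0 to 84.4%). In the 8.2.4.2 equation age enters once, with no interaction with group or visit, so the model cannot express a vaccine response that differs by age.

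**5. What is missing in the evaluable population?** SAP 5.2 admits a child for the primary endpoint only with a Visit 6 draw 28 to 42 days after dose 3 (criterion 4) and a valid, determinate result for the analysis in question (criterion 5). Children without a Visit 6 result are therefore outside the set. At most, a child could lack one strain's result if membership is not decided strain by strain. A MAR analysis there has essentially nothing to fill in.

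**The case against.** **SAP 8.2.1 may mean a different model.** It refers back to 7.1, not to 8.2.4.2, and names the evaluable population where 8.2.4.2 names mITT. A reader might infer that the promised analysis *is* the pooled log-titer model; the documents never say so, and the differing populations count against it. This stands as a correction to that inference, but it does not fill the gap: if a separate model was intended, nothing about it is specified.

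**The model could be fitted to the 0/1 indicator.** A reader might go further and say that such a fit necessarily gives invalid intervals. The documents do not support that. No section proposes the fit, and no expected response rates are given. As a rough guide, take the single-sample interval p ± 1.976·√(p(1−p)/149) at n = 150, with *assumed* rates:

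| Responders | Normal-theory interval | Exact interval |
|---|---|---|
| 90/150 (60%) | 52.1 to 67.9% | 51.7 to 67.9% |
| 120/150 (80%) | 73.5 to 86.5% | 72.7 to 86.1% |
| 146/150 (97.3%) | 94.7 to 99.9% | 93.3 to 99.3% |
| 148/150 (98.7%) | 96.8 to 100.5% | 95.3 to 99.8% |
| 150/150 | zero width | 97.6 to 100% |

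The interval fails only near the boundary. These are also not MMRM intervals: a variance shared across groups would prevent zero width unless the control group showed no variation either. This is a caution about one possible fallback, not the basis of the point.

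**Other supportive analyses exist.** SAP 8.2.1 repeats the by-stratum proportions in mITT, and 8.2.4.1 tabulates missingness against covariates. Both are useful. The first uses observed results only and the second estimates no proportion, so neither relaxes MCAR.

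**The consequence is limited.** The study is descriptive and the MMRM is conditional on testing all strains. Both statements are correct and bound the size of the point.

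**Conclusion.** The point holds. Under full testing, the plan promises an MMRM of the primary endpoints but specifies no model that yields a proportion at or above LLOQ by strain and age stratum. The one specified MMRM differs in outcome scale, age level and population, and cannot stand in for it. Placing the analysis in the evaluable population leaves it with essentially no missing Visit 6 result.

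The primary proportions and their exact intervals do not change, and no test or decision rule is involved. What is lost is the only planned check on those proportions that relaxes MCAR. The mismatch follows from the text alone; the titer sets, stratum pairs and response rates above are assumed values used to show its nature. No size of bias can be stated, because the documents give neither an expected rate of missing assay results nor expected response rates. The change should be made before unblinding but does not threaten the study's validity.

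**What to change.** Choose one and say so in SAP 7.1 and 8.2.1 and in Protocol 9.2.

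**Option A, keep a sensitivity analysis of the primary endpoints.** Replace the MMRM reference with a MAR analysis that returns the proportion at or above LLOQ for each strain, group and age stratum. Run it in mITT, or another set that keeps children with a missing Visit 6 result. Two workable forms:

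- a likelihood-based logistic repeated-measures model of the indicator over visits, fitted within stratum; or
- imputation of missing log titers from the child's other visits within stratum and group, with values below LLOQ treated as censored, then dichotomised at the strain's LLOQ and combined on a bounded scale.

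SAP Version 2.0 records that multiple imputation analyses were removed, so the second form needs a sentence explaining why imputation is used here. Report the result beside the primary and mITT proportions.

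**Option B, withdraw the claim.** Relabel the 8.2.4.2 MMRM as a sensitivity analysis for the GMT only, delete the statements that an MMRM supports the primary endpoints, and state that the primary proportions rest on MCAR.

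Cost: a few lines in the SAP and a conforming line in the protocol. Option A adds modest programming; Option B adds none. Neither needs new data.
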